6.12.4 Adverse Events

An adverse event (AE) will be defined as any AE, regardless of relationship to study drug, that occurs on or after the date of randomization and up to 30 days after the last dose. An event with a reported onset date after the subject has signed the informed consent document but prior to the date of randomization will be considered a pre-treatment event. Treatment-emergent adverse events (TEAEs) are defined as AEs whose onset occurs, severity worsens or intensity increases after receiving the study medication and up to 30 days after the last dose. Treatment-related

adverse events will be defined as treatment-emergent AEs which were identified by the investigator to be related to study drug.

Treatment-emergent adverse events will be summarized using the latest Medical Dictionary for Regulatory Agencies (MedDRA) coding dictionary. In general all AEs will be tabulated at each of the following levels by treatment group and overall: overall summary (subject with at least 1 AE), the MedDRA system organ class (SOC), the MedDRA high level term (HLT), and the MedDRA preferred term (PT). Tabulations at each level of a term will present count (n) and percentage of subjects reporting any event for that term. Subjects reporting more than one occurrence for the term (level) being summarized will be counted only once. Summaries involving severity (or relationship to study drug) will use the most severe (or most related) event when a subject has more than one event for a term. If the severity level of an AE is missing, the intensity of AE is considered to be severe.

Adverse events will be summarized as follows:

- A high-level summary of AEs which include the numbers and percentages of subjects for the following categories:
 - Any TEAE, any treatment-related TEAE, any TEAE leading to study drug withdrawal, any treatment-emergent serious adverse event (SAE), any treatment-related SAE, and any death.
- All treatment-emergent/ treatment-related treatment-emergent AEs.
- Treatment-Emergent Adverse Events by System Organ Class.
- Treatment-Emergent Adverse Events by Preferred Term.
- All TEAEs by relationship to study drug.
- All treatment-emergent/ treatment-related treatment-emergent AEs for subjects in each of the following subgroups:
 - Baseline Renal function.
 - Prophylactic medication taken.
- All treatment-emergent/treatment-related treatment-emergent AEs by MedDRA system organ class and high level term versus severity.
- Rash treatment-emergent/ treatment-related treatment-emergent AEs.
- Treatment-emergent/ treatment-related treatment-emergent serious AEs.
- Treatment-emergent/treatment-related treatment-emergent AEs Leading to Study Drug Withdrawal.
- Treatment-emergent/treatment-related treatment-emergent serious AEs Leading to Study Drug Withdrawal.
- All pre-treatment AEs.

The following listings will also be provided:

- All unique MedDRA terms.
- Adverse Events Leading To Study Drug Withdrawal During Treatment Period.

- Serious Adverse Events.
- Adverse Events Resulting in Deaths.

The number of AEs per 100 subject-years will be displayed for each level of summarization in all AE Tables. This calculation counts all episodes of an AE, including multiple events for the same subject. For a given treatment total patient-years (PY) of exposure will be calculated by summing across all subjects total number of days on the treatment and dividing by 365.

6.12.5 Clinical Laboratory Evaluations

Laboratory data include hematology, chemistry, and urinalysis variables. Laboratory data will be summarized at baseline and each post-baseline visit. The laboratory analyses will be performed on values obtained on study and no more than 7 days after last dose of study drug. For Hematology and Urinalysis since laboratory assessments are done only at screening, only baseline descriptive summaries will be provided.

6.12.5.1 Mean Change from Baseline

For serum chemistry laboratory variables, descriptive statistics will be presented for baseline, post-baseline, and change from baseline.

6.12.5.2 Markedly Abnormal Laboratory Values

For chemistry serum laboratory variables, the number and percentage of subjects with at least one markedly abnormal value at each post-baseline visit and the end of study will be presented. In addition, the number and percentage of subjects with any markedly abnormal value for serum chemistry variables will also be presented at each post-baseline visit.

Criteria for identifying markedly abnormal values have been established by Takeda Pharmacovigilance and Clinical Science Departments, and values meeting the criteria will be listed by subject.

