3.2 Study Design

This is a phase 3B multicenter, randomized, double-blind, active-controlled study designed to evaluate the CV safety of febuxostat compared with allopurinol in subjects with gout and significant CV comorbidities. Approximately 7500 subjects will be randomly assigned to study drug treatment.

The overall duration of the study is dependent on the number of predefined MACE. The length of the study is expected to be approximately 9 years. The length of study participation for each subject will vary due to the event driven study design. This study is designed to have a maximum of 624 MACE.

On Study Day 1, eligible subjects will be randomized in a 1:1 ratio to receive either febuxostat once daily (QD) or allopurinol QD. Randomization will be stratified based on baseline renal function (normal renal function or mild renal impairment versus moderate renal impairment). Baseline renal function will be defined using the following criteria based on estimated creatinine clearance (eCLcr):

- Normal renal function: defined as an eCLcr ≥ 90 mL/min.
- Mild renal impairment: defined as an eCLcr 60 to 89 mL/min, inclusive.
- Moderate renal impairment: defined as an eCLcr 30 to 59 mL/min, inclusive.

where estimated creatinine clearance (eCLcr) is calculated using the Cockcroft-Gault formula corrected for ideal body weight (IBW); IBW is 50 kg for males and 45.5 kg for women, plus 2.3 kg for each inch in height >5 feet (60 inches)]:

[figure not shown]
$$eCLcr = \frac{(140 - \text{Age}[\text{yr}]) \times (\text{IBW}[\text{kg}]) (\text{women multiply by } 0.85)}{72 \times (\text{serum creatinine} [\text{mg/dL}])}$$

Subjects randomized to febuxostat will initially receive the 40 mg dose QD. Subjects will remain on 40 mg for the remainder of the study if their serum uric acid (sUA) is <6.0 mg/dL at the Week 2 Visit. If their sUA is ≥ 6.0 mg/dL at the Week 2 Visit they will receive febuxostat 80 mg QD at the Week 4 visit, and will remain on this dose for the remainder of the study.

Subjects randomized to allopurinol who have normal renal function or mild renal impairment will initially receive allopurinol 300 mg QD with the dose increased in 100 mg increments monthly until either a sUA <6.0 mg/dL or an allopurinol dose of 600 mg QD is achieved. Subjects randomized to allopurinol who have moderate renal impairment will initially receive allopurinol 200 mg QD with the dose increased in 100 mg increments monthly until either a sUA

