6.12.6 Vital Signs

Descriptive statistics for baseline, post-baseline, and change from baseline will be computed by treatment group for all vital sign parameters (pulse rate, systolic blood pressure, and diastolic blood pressure). Data collected from baseline and up to 7 days after a subject's last dose of study drug will be included.

For each vital sign parameter, the number and percentage of subjects with at least one markedly abnormal value at each post-baseline visit and the end of study will be presented. In addition, the number and percentage of subjects with any markedly abnormal value for a vital sign parameter will also be presented at each post-baseline visit. Listing of Markedly Abnormal Laboratory Values will also be presented.

6.12.7 12-Lead ECGs

The number and percentage of subjects in each overall ECG interpretation category (normal, clinically significant abnormal, non-clinically significant abnormal) at baseline and Final Visit/ Early Termination will be summarized. Percentages will be based on the number of subjects with values at each visit. Data collected from baseline and up to 7 days after a subject’s last dose of study drug will be included.

In addition, shift tables showing the number of subjects with normal, clinically significant abnormal, or non-clinically significant abnormal ECG interpretation results at post-baseline visit will be provided.

For the ECG interpretation summaries, if a subject has multiple interpretations at a particular visit, the most significant result will be selected for summary.

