8.0 LIST OF APPENDICES

Appendix A Criteria for Identification of Markedly Abnormal Laboratory Values

Chemistry - Criteria for Markedly Abnormal Values

Parameter (Units)	Low Abnormal	High Abnormal
Albumin (g/dL)	≤2.4	–
Alkaline Phosphatase (IU/L)	–	≥1.5 x ULN
ALT (IU/L)	–	(a) ≥3 x ULN (b) ≥5 x ULN (c) ≥10 x ULN (d) ≥20 x ULN (e) ≥3 x ULN and Total Bilirubin >1.5 x ULN and (f) ≥3 x ULN and Total Bilirubin >2 x ULN
AST (IU/L)	–	(a) ≥3 x ULN (b) ≥5 x ULN (c) ≥10 x ULN (d) ≥20 x ULN (e) ≥3 x ULN and Total Bilirubin >1.5 x ULN and (f) ≥3 x ULN and Total Bilirubin >2 x ULN
Total Bilirubin (mg/dL)	–	≥2.0
Bicarbonate (mEq/L)	≤17	≥41
BUN (mg/dL)	–	≥31
Calcium (mg/dL)	≤7.0	≥12.0
Chloride (mEq/L)	≤79	≥121
Creatinine (mg/dL)	–	≥1.5 and increased from baseline by ≥0.3
Glucose (mg/dL)	≤49	≥301
Inorganic Phosphorus (mg/dL)	≤1.5	≥9.0
LDH (IU/L)	–	≥3 x ULN
Potassium (mEq/L)	≤2.9	≥5.9
Sodium (mEq/L)	≤124	≥151
Total Cholesterol (mg/dL)	–	≥350 and increased from baseline by ≥100
Total Protein (g/dL)	≤4.5	–
Triglyceride (mg/dL)	–	≥2 x ULN and increased from baseline by ≥100

ALT=alanine aminotransferase, AST=aspartate aminotransferase, BUN=blood urea nitrogen, LDH=lactate dehydrogenase, ULN=upper limit of normal.

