Appendix B Criteria for Identification of Markedly Abnormal Vital Sign Values

Vital Signs - Criteria for Markedly Abnormal Values

Parameters (Units)	Low Abnormal	High Abnormal
Systolic Blood Pressure (mm Hg)	<85 or drop >30 From Baseline	>180
Diastolic Blood Pressure (mm Hg)	<45 or drop >20 From Baseline	>110
Pulse (Beats/min)	<50	>120

Baseline is defined as the last measurement prior to the first dose of study drug.

ELECTRONIC SIGNATURES

Signed by	Meaning of Signature	Server Date (dd-MMM-yyyy HH:mm 'UTC')
PPD 	Biostatistics Approval	23-Feb-2017 21:59 UTC
	Clinical Science Approval	23-Feb-2017 23:21 UTC
	Pharmacovigilance Approval	24-Feb-2017 19:38 UTC

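### Markedly abnormal counts for absolute-limit parameters mix subjects past the limit at baseline with new cases, and the low blood pressure flag merges level with drop

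*SAP*

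**What the plan says.** For serum chemistry, SAP 6.12.5.2 presents "the number and percentage of subjects with at least one markedly abnormal value at each post-baseline visit and the end of study". SAP 6.12.6 uses the same construction: "For each vital sign parameter, the number and percentage of subjects with at least one markedly abnormal value at each post-baseline visit". Neither section conditions the count on baseline status, and neither states a denominator. Section 6.12.7 does state one for the ECG percentages.

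Appendix A treats its analytes in two ways. Creatinine needs a level and a rise ("≥1.5 and increased from baseline by ≥0.3"), as does total cholesterol ("≥350 and increased from baseline by ≥100"), and triglyceride is handled likewise. Every other analyte, including BUN, glucose, potassium, alkaline phosphatase, ALT and AST, has limits on the post-baseline value alone.

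In Appendix B the high blood pressure limits and both pulse limits are absolute. Low systolic pressure is "<85 or drop >30 From Baseline" and low diastolic pressure is "<45 or drop >20 From Baseline". The reference is one reading: "Baseline is defined as the last measurement prior to the first dose of study drug".

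**The concern.** A reader of a post-baseline abnormality table in a safety trial usually wants to know how many subjects became abnormal after starting drug. The SAP applies that logic to adverse events in 6.12.4 and to three analytes in Appendix A, but not to the other analytes or to the absolute vital-sign limits. Creatinine and BUN are both renal markers, yet only creatinine is protected from pre-existing abnormality. One part of the randomised population is defined in 3.2 by "Moderate renal impairment: defined as an eCLcr 30 to 59 mL/min, inclusive", so some subjects may plausibly have BUN past the limit before the first dose.

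Subjects abnormal throughout are expected equally in both arms. They raise both percentages and shrink the ratio between them.

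The blood pressure issue is separate. Because level and drop are joined by an or, a systolic fall from 190 to 155 mm Hg is counted in the same low-abnormal row as a reading below 85. The row then cannot show how many subjects reached a low pressure.

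**Working it through.** The SAP states no expected rate for these tables, so there is no planned figure to reproduce. All rates and SDs below are assumptions, shown as ranges.

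**1. Dilution of the ratio**

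Let b be the share past the limit at baseline, s the share of those who remain past it, and p1 and p2 the new-abnormality rates in the two arms.

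- Tabulated ratio = [b·s + (1−b)·p2] / [b·s + (1−b)·p1]
- Tabulated difference = (1−b)·(p2 − p1)

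With p1 = 5%, p2 = 7.5% (true ratio 1.50) and s = 1:

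| b | Percentages | Ratio | Difference (points) |
|---|---|---|---|
| 0 | 7.5 / 5.0 | 1.50 | 2.50 |
| 5% | 12.125 / 9.75 | 1.24 | 2.38 |
| 10% | 16.75 / 14.5 | 1.16 | 2.25 |
| 20% | 26.0 / 24.0 | 1.08 | 2.00 |

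With p1 = 3%, p2 = 4.5% and s = 1, the ratio is 1.37, 1.30, 1.18, 1.11 and 1.05 at b = 1%, 2%, 5%, 10% and 20%. The difference goes from 1.5 to 1.2 points at b = 20%.

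Incomplete persistence weakens the effect. At b = 10%, s = 0.5 and 5% versus 7.5%, the ratio is (0.05 + 0.0675)/(0.05 + 0.045) = 0.1175/0.095 = 1.24, compared with 1.16 under full persistence.

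Among subjects not abnormal at baseline the ratio stays 1.50 in the first example for every b.

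**2. Chance of meeting the drop criterion with no true change**

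Take the baseline and visit readings as independent normal values around the same subject mean, with within-subject SD σ. Their difference has SD σ√2, so P(drop > c) = 1 − Φ(c / (σ√2)).

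| Criterion | σ (mm Hg) | c / (σ√2) | Flagged at one visit |
|---|---|---|---|
| Systolic >30 | 8 | 2.65 | 0.4% |
| | 10 | 2.12 | 1.7% |
| | 12 | 1.77 | 3.9% |
| | 15 | 1.41 | 7.9% |
| Diastolic >20 | 5 | 2.83 | 0.2% |
| | 7 | 2.02 | 2.2% |
| | 9 | 1.57 | 5.8% |
| | 10 | 1.41 | 7.9% |

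**3. Do other planned summaries close the gap?**

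- Laboratory shift tables (6.12.5.3) use the reference range. A subject above normal but below the marked limit at baseline, who later crosses that limit, stays high to high.
- Change from baseline (6.12.5.1 and 6.12.6) describes the distribution of changes, not the number of subjects newly crossing a marked limit.
- No shift table is planned for vital signs.
- Listings of markedly abnormal laboratory values are planned, but they give no between-arm summary of new cases.

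These summaries cover part of the gap only.

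**The case against.** The SAP never says these tables show what emerged on drug. It promises counts of post-baseline values past a limit, and the rule delivers them. No between-arm test of these data is planned; the amendment history in 6.14.2 records that such inference was removed. The tables give percentages, and the absolute difference barely moves. Randomisation balances the background in expectation, so neither arm is favoured. All of this stands, and it keeps the point small.

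Several stronger readings are tempting but unsupported:

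- **Blood pressure is flagged on any drop.** It is not. The drop must exceed 30 mm Hg systolic or 20 mm Hg diastolic. A true any-drop rule would flag about 50% at one visit under the model above.
- **All laboratory counts carry baseline disease.** Creatinine, total cholesterol and triglyceride already require a rise.
- **High glucose at baseline will be common because diabetes is a history item.** The limit is ≥301 mg/dL, and the SAP does not show how often it is exceeded. BUN is the more plausible example, and its baseline prevalence is also not given.
- **The low blood pressure row is mostly noise.** The model assumes no true change, so every flag in it is noise by construction. It cannot give the share of real flags that are noise.
- **Drug effects are hidden.** The ratio is diluted, its direction is kept, and the change and shift summaries show part of the picture.

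Restricting the count outright would also lose a subject who is just past a limit at baseline and then worsens greatly. That is a fair objection to exclusion, but not to showing both groups.

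**Conclusion.** The point holds as a reporting weakness in descriptive secondary safety tables. For absolute-limit parameters the counts in 6.12.5.2 and 6.12.6 mix continuing with new abnormality, and no other planned table fully separates them. In the first example, a true ratio of 1.50 would appear as 1.24 to 1.08 at 5% to 20% persistent baseline abnormality, while the difference falls only from 2.5 to 2.0 points. The size for any real parameter depends on baseline prevalence and persistence, which the SAP does not give; where few subjects are past the limit at baseline, the effect is small.

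For blood pressure, level and drop are merged in one low-abnormal flag measured against a single baseline reading. Chance alone could put about 0.4–7.9% of subjects past the systolic drop criterion at a visit, if within-subject SD is 8–15 mm Hg. The primary MACE inference is untouched. Priority is low.

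**What to change.** - In 6.12.5.2 and 6.12.6, report the counts for absolute-limit parameters split by whether the same criterion was met at baseline. The main row is subjects not meeting it at baseline, with those having a post-baseline value as denominator. Keep baseline-abnormal subjects in a separate row with their own denominator.
- For systolic and diastolic pressure, print the absolute-level and drop-from-baseline criteria as separate rows. The baseline split applies to the level row; a drop from baseline cannot be met at baseline. For the same reason creatinine, total cholesterol and triglyceride need no split.
- Leave every threshold in Appendices A and B as it is.

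The cost is a sentence or two in each section, a baseline flag and extra rows in existing table programs. The main row has a smaller denominator, and worsening among baseline-abnormal subjects appears only in the separate row, so that row must not be dropped.

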6.12.5.3 Shifts Relative to Normal Range

Shift tables showing the number of subjects with low, normal, or high values at each post-baseline visit according to the central laboratory's reference ranges will be presented.

6.12.6 Vital Signs

Descriptive statistics for baseline, post-baseline, and change from baseline will be computed by treatment group for all vital sign parameters (pulse rate, systolic blood pressure, and diastolic blood pressure). Data collected from baseline and up to 7 days after a subject's last dose of study drug will be included.

For each vital sign parameter, the number and percentage of subjects with at least one markedly abnormal value at each post-baseline visit and the end of study will be presented. In addition, the number and percentage of subjects with any markedly abnormal value for a vital sign parameter will also be presented at each post-baseline visit. Listing of Markedly Abnormal Laboratory Values will also be presented.

6.12.7 12-Lead ECGs

The number and percentage of subjects in each overall ECG interpretation category (normal, clinically significant abnormal, non-clinically significant abnormal) at baseline and Final Visit/ Early Termination will be summarized. Percentages will be based on the number of subjects with values at each visit. Data collected from baseline and up to 7 days after a subject’s last dose of study drug will be included.

In addition, shift tables showing the number of subjects with normal, clinically significant abnormal, or non-clinically significant abnormal ECG interpretation results at post-baseline visit will be provided.

For the ECG interpretation summaries, if a subject has multiple interpretations at a particular visit, the most significant result will be selected for summary.

6.13 Interim Analysis

This study is designed to have a maximum of 624 MACE composite events for assessing non-inferiority of febuxostat relative to allopurinol with regard to cardiovascular risk assuming a true hazard ratio of 1.0 and 90% power. Interim analyses will be conducted when approximately 25%, 50% and 75% of the events or equivalently approximately 156, 312, and 468 events have occurred, followed by a final analysis. In this group sequential trial with 4 equally-spaced analyses and a one-sided overall significance level of 0.025, the Lan-DeMets alpha spending approach with an O’Brien-Fleming stopping boundary will be used. Table 6.c displays the projected critical boundaries and the overall 1-sided 2.5% significance level spending at each interim analysis obtained from the O’Brien-Fleming spending function. [contact] was used to determine the critical boundaries.

Table 6.c O’Brien-Fleming Spending Function

Interim Look	Information Fraction	Critical Boundary	Alpha Spending at Each Interim	Cumulative Alpha Spending
1	156/624 = 0.25	4.333	0.000	0.000
2	312/624 = 0.50	2.963	0.002	0.002
3	468/624 = 0.75	2.359	0.008	0.010
4	624/624 = 1.00	2.014	0.015	0.025

Therefore, at the 3 interim and at the final analyses, one-sided confidence intervals for the hazard ratio of febuxostat relative to allopurinol for the primary endpoint will be constructed using critical values obtained using the Lan-DeMets -O’Brien-Fleming alpha spending function. At each analysis, if the upper confidence limit of the hazard ratio is ≤ 1.3 , the study will be stopped and the non-inferiority of febuxostat relative to allopurinol with regard to cardiovascular risk will be declared. If non-inferiority is declared at an interim analysis, subsequent analyses of the primary endpoint will be considered sensitivity analyses.

Periodically during the course of the study, a blinded assessment of the annual adjudicated MACE rate will be made. The number of subjects planned to be enrolled in this study was based

on an event rate of 2.8%, which was based on limited information. Based on the overall blinded MACE rate observed, an assessment will be made to determine whether or not to adjust the number of subjects planned for enrollment.

At the DMC meeting on ^{PPD} [REDACTED], the 75% interim analysis results based on 468 adjudicated MACE for the primary MACE endpoint to assess cardiovascular safety was reviewed by the DMC. At the DMC meeting on ^{PPD} [REDACTED], the DMC informed Takeda that the non-inferiority criterion for the primary endpoint was met at the 75% interim analysis conducted in ^{PPD} [REDACTED]. According to the study design, the study should have been stopped and the non-inferiority of febuxostat relative to allopurinol with regard to cardiovascular risk should have been declared. However the DMC recommendation was to continue the trial without modification until the maximum 624 unique events were achieved to further assess all cause mortality (which was not a protocol specified endpoint) and CV mortality (which is specified only as a component of the MACE endpoint). Takeda agreed to follow the DMC recommendation and continue the study.

Based on the group sequential design, the 75% interim analysis will be the primary analysis for the primary MACE endpoint for the purpose of statistical inference. The continuation of the study to protocol-specified maximum events (624 unique MACE) is for the assessment of all cause mortality and CV mortality. The analyses of all cause mortality and CV mortality with and without death events after discontinuation of treatments will be added to the end of study analysis. An updated sensitivity analysis for the primary MACE endpoint based on 624 unique MACE will also be conducted to provide additional supportive evidence for the primary endpoint.

